3.2.2 Secondary Outcome Measures

Secondary Outcomes (Aim 2):

Fluid adherence. Interdialytic weight gain, a fluid intake measure, predicts stability; it is routinely recorded by facilities at each session.

Dialysis adherence. Data regarding dialysis adherence¹²⁵ are routinely collected by all hemodialysis facilities at each session. We will use three measures: number of minutes of prescribed dialysis time missed per week, number of missed sessions per week and total missed session time.

Patient symptoms. We will create a Patient Symptom Burden measure combining: symptom frequency and severity for each of the following symptoms that are often indicative of IDH, if they occur during or after the dialysis session (not pre-dialysis): nausea, vomiting, abdominal pain, dizziness, muscle cramps, headache, chest pain, shortness of breath, palpitations, diaphoresis, and blurred vision (as listed in the digital Chairside symptom module that is completed every session by the nurse. Symptoms listed on the KDQOL survey (see below) will be added to the patient symptom burden measure to supplement the scores obtained from the symptom module. We will also calculate the proportion of sessions with each symptom using date and time of session.

The nurse does a nursing assessment of the patient at each dialysis session and records symptoms (which are by definition reported by the patient) in the Chairside documentation system using structured fields and free text fields as needed. The structured fields include options for the nurse to record the location, duration, and severity of the symptom (including cramping) based on patient complaints. Symptom frequency and severity will be stated by the patient and recorded by the nurse during the assessment.

Additionally, after consultation with FMCNA's patient advisory committee and our patient partners, we have created a survey question to assess recovery time that builds on past research.¹²⁶

The patient recovery time measure is based on a question to be posed by the patient care technician or nurse on a weekly basis (not occasionally). This question, which will appear in the Chairside documentation system as part of the intake screen, is as follows:

After your last dialysis session, how long did it take you to recover enough to do the things you normally do on a non-dialysis day?

- a. Within minutes
- b. By the time I returned home
- c. After a short nap (30 minutes or less)
- d. After a long nap (over 30 minutes)
- e. By bed time
- f. By the next morning
- g. Before the next scheduled dialysis session
- h. Did not recover before the next scheduled dialysis session
- i. Patient unable or declined to answer

Furthermore, the Chairside system will require completion of this question once a week before the staff member begins the dialysis session. The patient care technicians and nurses will be trained prior to study start to record these data.

Responses to this variable will also be used as a secondary outcome for patient symptoms, alone and in combination with the patient symptom burden measure described above. This question will be asked once per week of every patient in the study.

Quality of life. Quality of life is a patient-reported outcomes, which is “any report of the status of a patient's health condition that comes directly from the patient, without interpretation of the patient's response by a clinician or anyone else.”¹²⁷ PRO instruments can be interviewer-administered, self-administered, computer-administered or interactively administered.¹²⁷ We will use the 36-item Kidney Disease Quality of Life (KDQOL™-36 Version 1),^{128, 129} which has good internal consistency based on alpha scores.¹²⁹ This instrument is required annually for US hemodialysis patients.¹³⁰ The quality of life survey, the Kidney Disease Quality of Life (KDQOL™-36 Version 1), is intended to be completed on at least an annual basis. KDQOL results will be provided twice for each patient from surveys available as follows: 1) The latest survey within 12 months prior to the start of the study intervention and 2) the earliest survey within 12 months after the start of the intervention. As is current procedure at FMCNA, the measure of quality of life is based on a self-administered survey by providing a paper copy to the patient to complete during treatment or at home. If a patient needs assistance, the Social Worker will assist patients during treatment or via phone in completion of the survey as needed or desired.

Hospitalization. These data will be gathered from FMCNA records for all patients. Hospitalizations within the study period will be calculated. Secondary analyses of this outcome will assess hospitalizations by cause using hospital discharge diagnosis (e.g., fluid-related or cardiovascular causes, COVID-19), number of hospitalizations per patient, and length of hospitalization.

Mortality. These data will be gathered from FMCNA patient records.

3.2.3 Behavioral Outcomes (Behavior Change Measures)

Patient session instability prevention behavior. Once per week, the patient care technician or nurse will also record data regarding patient participation in their fluid removal goals for a specific session. The question, which has already been incorporated into FMCNA's Chairside documentation system for study purposes, is as follows:

“Did the patient make a request today regarding their fluid removal goal?

- No
- Yes, requested more than the recommended fluid removal goal
- Yes, requested less than the recommended fluid removal goal”

Using these data, we will create a patient-level measure of instability prevention behavior that sums the number of requests regarding fluid removal made by each patient, along with weighting based on the appropriateness of the request. Appropriateness of the patient request will be determined based on the “direction of patient request” combined with assessment of clinical factors.

Fluid practice patterns measure. We will create a patient-level measure of fluid management practice patterns that combines the frequency of the following behaviors: (1) Number of times a patient's post-dialysis target weight was changed, (2) patient average treatment time delivered, (3) patient average session ultrafiltration rate, (4) number of changes in number and categories of BP medications patient is taking, (5) use of cool dialysate (based on average dialysate temperature for the session), and (6) whether the patient switched to home dialysis (peritoneal dialysis or home hemodialysis, using treatment modality change) during study period. These are practices that could change as a result of the interventions that may explain intervention effects in the primary and secondary outcomes.

3.2.4 Importance of secondary outcomes, and their role in the analysis and interpretation of study results

We will analyze the impact of the interventions on each of the secondary outcomes; thus, the effectiveness of the interventions will be assessed in relation to both the primary and the secondary outcomes. The study has the following patient-centered secondary outcomes:

Interdialytic weight gain. Interdialytic weight gain, a measure of fluid gains between dialysis sessions, which is measured every session. This outcome is important to patients as high fluid gains are linked to unpleasant symptoms such as bloating and shortness of breath.¹³¹ High fluid gains are associated with fluid overload, which is a leading cause of hospitalization in dialysis patients.^{132, 133} High fluid gains are also associated with mortality risk, particularly from cardiovascular causes.^{134, 135} Interdialytic weight gain is a top-20 priority outcome (of 33 ranked) for dialysis patients.⁸⁵

Patient symptoms during the dialysis session based on patient reports of their physical experiences and sensations. This is a priority outcome for patients.¹³⁶ This is further justified since HD patients are burdened by negative symptoms. Patients report severe fatigue in 50% of HD sessions, and cramping in 30%.⁴⁰

Patient symptoms after the session in the form of recovery time, which represents both post-dialysis fatigue and functioning. More than 40% of patients feel that they have not fully recovered even after returning home after HD.⁴⁰ As an indicator of both fatigue/energy and dialysis-free time, this is one of the most important outcomes to hemodialysis patients (1st and 4th of 33 ranked), and more important to patients than healthcare providers.^{85, 137}

Health-related quality of life, a patient-reported outcome which will be measured before and after the intervention which has been provided as a key example of a patient-centered outcome by PCORI.¹³⁸ HRQOL is a longer-term measure that reflects symptom patterns and other key life dimensions including physical functioning, emotional well-being, pain, and energy levels.¹³⁹ The human suffering represented by low HRQOL predicts outcomes that matter to patients, including hospitalizations¹⁴⁰ and mortality.^{140, 141}

Hospitalizations, which represent a period of heightened symptoms and lost functioning among patients; patients describe hospitalizations as extremely distressing, and hospitalizations are a top-21 priority outcome for dialysis patients (of 33 ranked).⁸⁵

Mortality, which has been provided as a key example of a patient-centered outcome by PCORI.¹³⁸

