5.4 TREATMENT ASSIGNMENT PROCEDURES

5.4.1 Randomization Procedures

The 20 hemodialysis facilities will be randomized to the four intervention combinations of the 2x2 factorial design, assigning 5 facilities to each of the 4 combinations (both provider education and patient activation using peer mentoring; provider education alone; patient activation alone; and neither intervention). Facilities will be stratified by geographic region and socio-economic status to ensure treatment balance on those factors.

With regard to peer mentoring only, we will randomly select patients who are not vulnerable and have not opted out of the study in succession, until approximately 30 English-speaking patients in a facility accept peer mentoring. Patient randomization will be stratified by treatment shift. Every time a patient declines to participate, we will choose another patient randomly until the enrollment target is reached. Patients entering a facility randomized to the patient activation intervention during weeks 1-18 of the 24-week intervention period will be added to the list of patients eligible for peer mentoring from which patients are randomly selected for peer mentoring. We anticipate that 15-20% of patients in the study facilities will be replaced by new patients during the 11-month study period due to mortality, change in ESRD treatment modality (e.g., a kidney transplant), or changing facilities.

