Aim 2. Test and compare the effects of the two HD facility-level interventions on secondary patient-centered clinical outcomes, including: patient symptoms, fluid adherence, dialysis adherence, quality of life, hospitalizations and mortality over the same timeframe.

Aim 2 incorporates six outcome measures: (1) patient symptoms (including a patient burden measure, dialysis recovery time, and proportion of sessions with each symptom), (2), fluid adherence (inter-dialytic weight gain), (3) dialysis adherence, (4) quality of life, (5) hospitalization (all-cause and by specific cause), and (6) mortality (all-cause and by specific cause), with will be analyzed at the individual level and summarized at the facility level. Each

will use a model format appropriate to the outcome type, but will otherwise follow the model strategy, including the secondary analyses, described for Aim 2 above. This includes censoring of patient data while they are at another facility. The fluid adherence (Interdialytic weight gain), symptom and quality of life analyses, based on continuous outcome measures, will be carried out using mixed models (the MIXED procedure of SAS). Note that the quality of life analyses will be based on data from two time points, one before intervention and one during intervention, rather than session-specific data as analyzed for the other outcomes. Analyses of missed or shortened HD sessions will employ logistic regression for longitudinal data, as in Aim 2. Analyses of hospitalization and mortality will use logistic regression for individual level data. As part of these models, we will test IDH-related variables (e.g., recent IDH, frequency of IDH in the past month) as potential predictors. In each case, the appropriate regression diagnostics will be used to assess model fit.

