Mediation Analyses. Mediation analyses will be conducted for each of the six patient-level secondary outcomes: (1) patient symptoms; (2) fluid adherence (inter-dialytic weight gain); (3) dialysis adherence; (4) quality of life; (5) hospitalization; and (6) mortality. Depending on the secondary outcome in question, the following variables will be examined as potential mediators.

Mediators of the Secondary Outcomes: Patient-level variables to be examined include: (1) patient session instability prevention behavior; (2) fluid management practice patterns; (3) number and categories of blood pressure medications patient is taking; (4) fluid adherence (inter-dialytic weight gain); (5) dialysis adherence; (6) patient symptoms (symptom burden and recovery time); (7) hospitalizations for cardiovascular or fluid-related causes in the past 4 weeks; and (8) quality of life.

The following *session-level* variables will be variables will be transformed into patient-level variables for the appropriate time period depending on the secondary outcome under examination, and assessed for mediation effects: (1) treatment time delivered; (2) average session UFR; (3) cooled dialysate used; (4) sodium modeling used; (5) ultrafiltration modeling used; (6) ultrafiltration variability for whole session, or up until incident of IDH (if IDH occurs) (ex: difference between the highest and lowest UFR, standard deviation of the UFR measures, the square root of the mean squared differences of successive UFR measures); (7) sitting-to-standing difference in SBP (Orthostasis at beginning of session); (8) starting SBP; (9) slope of changes in SBP over 30 minute intervals for whole session, or up until incident of IDH (if IDH occurs); (10) values of lowest and highest SBP readings as a measure of range of SBP during the dialysis session; (11) patient requests regarding fluid removal; (12) fluid adherence (inter-dialytic weight gain) prior to this session; (13) achievement of post-dialysis target weight; and (14) session instability (IDH).

Aim 3. Identify factors associated with successful implementation of the Dialysafe interventions, and ways in which implementation may influence intervention effectiveness.

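### The patient behaviour measure is a weighted sum with no time denominator, so as a mediator of mortality it is tied to death through weeks observed

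*Combined protocol and SAP*

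**What the plan says.** **The measure (3.2.3).** "Once per week, the patient care technician or nurse will also record data regarding patient participation in their fluid removal goals". The patient-level score "sums the number of requests regarding fluid removal made by each patient", each request being weighted by how appropriate it was. Appropriateness depends on the direction of the request and on clinical factors, but no weights are given, and there is no denominator, offset or window. The fluid practice measure in the same section mixes averages (treatment time, ultrafiltration rate) with counts (target-weight changes, blood-pressure-medication changes).

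**Observation time.** Sections 4.1 (VI) and 7.2 enrol new patients until 8 weeks before the 24-week intervention ends, that is, to week 16. Section 7.2 hands out information sheets to new patients every two months, and only to those at least 30 days in the clinic; the weekly question runs only between the start and stop dates of the study order. Section 5.4.3 uses data only up to departure. Section 5.4.1 expects that "15-20% of patients in the study facilities will be replaced by new patients during the 11-month study period".

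**The use (11.4, Aim 2).** "Mediation analyses will be conducted for each of the six patient-level secondary outcomes", mortality among them. The patient-level mediator list opens with "patient session instability prevention behavior; (2) fluid management practice patterns". "Analyses of hospitalization and mortality will use logistic regression for individual level data", with no person-time term described. Wording about a suitable time period covers only the session-level mediators; among the patient-level ones, only prior hospitalisations carry a window (four weeks).

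**The chain (11.4, Aim 1).** The intervention must predict the outcome, then the mediator. Finally, the intervention effect must shrink once the mediator is added, and the mediator must be significant. Causal interpretation is disclaimed.

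**The concern.** A sum of weekly records grows with the number of weeks recorded. Two patients who behave identically get different scores if one is observed for longer. For mortality the problem is sharper, because death itself ends the counting: the mediator is partly a consequence of the outcome. The last step of the mediation chain could then be met by the bookkeeping alone, and an effect that works through some other route could be credited to patients' fluid-removal requests.

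Elsewhere the plan mostly does normalise: adherence is per week (3.2.2), weight gain is a percentage of sessions, and recovery time and symptom burden are patient means (11.2). This measure and the count components of the practice measure lack that step.

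**Working it through.** The documents give no figure for this measure, so there is none to reproduce.

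**Inputs from the documents:** annual mortality 17.5% (2.1.3; 15-20% in 9.3); 36 weeks tracked after baseline (4.1); 1,200 patients (section 5), so 600 per side of each factor; significance level 0.05 (11.2).

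**Assumptions, not in the documents:** 0.05-0.5 requests per week; between-patient coefficient of variation 0-1.5; up to 30% a year leaving alive; up to 30% late entry; the weights. Clustering and covariates are ignored.

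**1. Late entry.** A week-16 entrant has at most 36 − 16 = 20 weeks. 20/36 = 0.56, so the sum is 44% below that of an identical patient observed throughout.

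**2. Death.** Weekly hazard λ = −ln(1 − 0.175)/52 = 0.00370.
- Deaths by week 36: 1 − exp(−36λ) = 12.5%.
- Mean weeks observed in those who die: 1/λ − 36/(exp(36λ) − 1) = 270.3 − 252.7 = 17.6, or about 17 complete weeks. Survivors have 36.
- The expected sum is rate × mean weight × weeks. At 0.2 requests per week and unit weights this is 0.2 × 17 = 3.4 in those who die and 0.2 × 36 = 7.2 in survivors, with no effect of requests.

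**3. Null simulation, unit weights** (300 trials per scenario; death regressed on arm and the score). The odds ratio per SD of the sum was 0.07-0.56, significantly protective in 94-100% of trials. The scenarios varied the request rate, patient variation, mortality of 15-20%, 24 or 36 weeks, exits and late entry.

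**4. Effect of the weights** (0.2 per week, coefficient of variation 1). Gap = 0.2 × mean weight × (36 − 17).

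| Weight if inappropriate | Share inappropriate | Mean weight | Gap, survivors minus deaths | OR per SD | Significant |
|---|---|---|---|---|---|
| 0 | 50% | 0.5 | 1.9 | 0.43 | 100% protective |
| −1 | 30% | 0.4 | 1.5 | 0.56 | 100% protective |
| −1 | 50% | 0 | 0 | 1.00 | under 1% |
| −1 | 70% | −0.4 | −1.5 | 1.79 | 100% harmful |

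**5. Reaching the mortality analysis.** Power for an intervention effect on 36-week mortality, 600 against 600, before any loss from clustering, is about 9% at hazard ratio 0.9, 25% at 0.8 and 52% at 0.7.

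**6. Full chain, unit weights, requests with no effect on death.**
- Intervention does not change requests: all steps passed in 0-0.5% of trials with no mortality effect, and in 1-3% at hazard ratio 0.7-0.8.
- Intervention lowers mortality (hazard ratio 0.7) and raises requests 1.5-fold: 47% of trials passed the first step, and every one of those passed the whole chain. About 45% of the arm effect was falsely credited to requests. In a second run under its own assumptions the mean arm log odds ratio fell from −0.37 to −0.18, about half. The share depends on the assumed spread of request rates.

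**7. Hospitalisation.** Admission does not end follow-up, so longer observation raises both the sum and the chance of an admission. At two admissions per patient-year (9.3) the association was significantly positive in 23-74% of trials, depending on assumptions, and significantly negative in none.

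**8. Remedies under the null.** Requests per observed week gave odds ratios of 0.97-1.02, so the bias goes. Its tests remained liberal: 8.5-10.5% significant in one set of runs and up to 32% in another, split between directions, because rates from short follow-up are noisy. A fixed early window with only later deaths gave 2-8% (8 weeks) and 3-8.5% (12 weeks).

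**The case against.** The strongest reply is that this is an exploratory analysis behind a gate. The trial is not powered for death, mediation is dropped unless an intervention predicts the outcome, and causal reading is disclaimed. Mediators are also to be chosen according to the outcome, and the same request data appear among the session-level mediators, where an outcome-specific period is foreseen. Much of this stands: a misleading mortality mediation result is unlikely to be produced at all. But the gate does not repair the analysis once it is reached (step 6). The period wording is not applied to the summed score. And the disclaimer sits beside a stated aim of finding mechanisms of action.

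Several stronger readings are tempting and are not supported:
- *The measure is an unweighted count that must look protective.* It is weighted, the weights are unstated, and they set the direction (step 4).
- *The plan would almost always report a false mechanism.* The 94-100% refers to the mediator term alone; the full chain passes far less often.
- *Hospitalisation is biased in the same direction.* It runs the other way (step 7).
- *The measure is confounded as a between-arm behavioural outcome.* Arms share the same entry and follow-up rules, so without differential retention unequal observation mainly adds noise.

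For the practice measure, the plan speaks of combining frequencies, which could be read as rates. Its count components were not simulated.

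**Conclusion.** The concern holds in a limited form. As defined, the score depends on weeks observed, and in a patient-level logistic model for mortality it is associated with death by construction. It is falsely protective when the weights are non-negative or positive on balance, and null or reversed when inappropriate requests carry enough negative weight. That the direction turns on unstated weights is itself a reason to complete the definition.

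The practical reach is narrow. The mortality analysis requires a mortality effect that the trial has about 9-52% power to show at hazard ratios of 0.9-0.7, before clustering. The damaging case is an intervention that lowers mortality and also raises requests: under the assumptions above, roughly 45-50% of the effect was then credited to requests with no causal link. The link between the sum and time observed follows from the definition. The sizes rest on assumed request rates, patient variation and weights, and on independence of patients.

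**What to change.** 1. In 3.2.3, define the measure as weighted requests divided by the number of weeks with a recorded answer, and state the weights.
2. Express target-weight changes and blood-pressure-medication changes in the practice measure per unit of observed time.
3. In 11.4, for mortality and hospitalisation mediation, measure the mediator over a fixed early window (for example the first 12 intervention weeks) in patients still under observation and event-free, and analyse only later events. State how the window applies to late entrants. The per-week rate alone is not enough, because its p-values stay somewhat liberal.

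No new data are needed; the change is a few sentences of definition. The price is lost events in this exploratory analysis. At 17.5% annual mortality and full entry at week 0, 1 − exp(−12 × 0.00370) = 4.3% die in the first 12 weeks, against 12.5% by week 36: about 52 of 150 deaths among 1,200 patients, or 35%. For hospitalisation at two admissions per patient-year, with a constant rate equal for all patients, exp(−2 × 12/52) = 63% would be admission-free at week 12, so about 37% of patients would drop out. A shorter window loses less; an 8-week window also held its error rate under the null for mortality.
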